**STATEMENT OF COMPLIANCE**

The trial will be conducted in accordance with International Conference on Harmonisation Good Clinical Practice (ICH GCP) and applicable United States (US) Code of Federal Regulations (CFR). The Principal Investigator will assure that no deviation from, or changes to the protocol will take place without prior documented approval from the Institutional Review Board (IRB), except where necessary to eliminate an immediate hazard(s) to the trial participants. All personnel involved in the conduct of this study have completed Human Subjects Protection and ICH GCP Training.

The protocol, informed consent form(s), recruitment materials, and all participant materials will be submitted to the IRB for review and approval. Approval of both the protocol and the consent form must be obtained before any participant is enrolled. Any amendment to the protocol will require review and approval by the IRB before the changes are implemented to the study. All changes to the consent form will be IRB approved; a determination will be made regarding whether a new consent needs to be obtained from participants who provided consent, using a previously approved consent form.

**1 PROTOCOL SUMMARY****1.1 SYNOPSIS**

Title:	Single-Use Negative Pressure Wound Therapy for Free Flap Donor Sites
Study Description:	This study will be a single-center, randomized, parallel-assignment clinical trial to assess the efficacy of using single-use negative pressure wound therapy (NPWT) devices on free flap donor sites. Subjects will be randomized to one of two treatment arms (NPWT single-use device vs traditional wound dressing).
Objectives:	Primary Objective: To assess the progression of wound healing from Baseline through 30 days.
Endpoints:	Primary Endpoint: Progression of wound healing, as measured by comparison of photographs of all subject wounds taken at post-operative Day 5, post-operative Day 14-21, and post-operative Day 30. Percentage skin graft take will be evaluated on Day 30 by blinded, independent raters.
Study Population:	It is anticipated that 20 subjects will be enrolled in this protocol. Potential subjects will be male or female adults over the age of 18 from the United States who are undergoing head and neck surgery requiring reconstruction with a free flap, for which the donor site will be covered with a split-thickness skin graft (i.e., radial forearm free flap or fibula free flap).
Phase:	N/A
Description of Study Intervention:	Treatment group: PICO Single Use Negative Pressure Wound Therapy System, a Class II negative pressure wound therapy powered suction pump  Control group: xeroform gauze, a traditional surgical dressing of xeroform gauze and padding
Study Duration:	Approximately 12 months
Participant Duration:	Approximately 14 days

## 1.2 SCHEDULE OF ACTIVITIES (SOA)

	Screening Day -7 to -1	Baseline Day of Surgery Day 0	POD 5 Day 5 ( $\pm 2$ )	POD 14 Day 14 ( $\pm 7$ )	POD 30 Day 30 ( $\pm 7$ )	End of Study
Procedures						
Informed consent	X					
Demographics	X					
Medical history	X					
Randomization		X				
Study intervention		X				
Wound photograph			X	X	X	
Blinded assessment of wound photographs						X
Concomitant medications	X	X	X	X	X	
Adverse events		X	X	X	X	

## 2 INTRODUCTION

### 2.1 STUDY RATIONALE

Various management options for free flap donor sites that require split thickness skin grafting exist. None has proven superior from both a patient care and a cost standpoint. Major complications occurring at these surgical sites include wound breakdown, tendon exposure, and loss of function. We seek to investigate the use of the PICO single-use negative pressure wound therapy device in these surgical sites and determine if it can yield superior results to simpler methods.

### 2.2 BACKGROUND

Many studies have addressed the use of negative pressure wound therapy (NPWT) in free flap donor sites with mixed results. It is well established that NPWT is safe and causes no harm, and no delay in healing. A previous study performed at UAB showed that NPWT in complex Head & Neck Surgery reconstruction is safe, including free flap donor sites. There have been studies that state the rate of tendon exposure is lower with NPWT in free flap donor sites, and studies that conclude there is no difference in complication rates. Current clinical practice is varied, often within a single institution.

While no studies of NPWT in free flap donor sites have noted inferior results with its use, a primary reason cited for not using it is cost. Traditional NPWT using canister-based vacuum devices adds significant cost. The PICO single-use NPWT device (Smith & Nephew) is a relatively inexpensive, low-profile dressing that does not require attachment to an external canister. It is battery-powered and disposable. Empiric use on our patients undergoing split-thickness skin-grafting to free flap donor sites shows good results with minimal intra-operative effort compared to traditional bandaging. We would like to prospectively investigate the use of this low-cost NPWT device and compare it directly to the traditional post-op dressing method.

## 2.3 RISK/BENEFIT ASSESSMENT

### 2.3.1 KNOWN POTENTIAL RISKS

All of the devices to be used in this study are FDA-cleared, commercially available, and will be used for their approved indications.

- *Risks associated with the PICO NPWT device:* Per the device labeling, PICO not intended for use with complex wounds with extensive undermining or tunneling, or wounds that exceed 25% of the dressing pad area. It is not intended for use with patients with malignancy in the wound bed or margins; previously confirmed or untreated osteomyelitis; non-enteric and unexplored fistula; use on necrotic tissue with eschar present; use over exposed blood vessels, nerves, or organs; exposed anastomotic sites. There is a small risk of superficial pain at the application site and with removal of this device.
- *Risks associated with xeroform dressing:* Per the device labeling, xeroform petrolatum dressing is not labeled for use with third degree burns; as having an accelerating effect on the rate of wound healing or epithelization; as a long-term, permanent, or no change-dressing, or as an artificial (synthetic) skin; as a treatment or cure for any type of wound. There is a small risk of superficial pain with removal of this device.

### 2.3.2 KNOWN POTENTIAL BENEFITS

All of the devices to be used in this study are FDA-cleared and will be used for their approved indications.

- *Benefits associated with the PICO NPWT device:* Per the device labeling, PICO is indicated for patients who would benefit from a suction device (negative pressure wound therapy) as it may promote wound healing via removal of low to moderate levels of exudate and infectious materials. Appropriate wound types include chronic, acute, traumatic, subacute and dehisced wounds, partial-thickness burns, diabetic or pressure ulcers, flaps and grafts, and closed surgical incisions.
- *Benefits associated with xeroform dressing:* Per the device labeling, xeroform petrolatum dressing is intended for use as a primary contact layer in dressing wounds such as lacerations, skin graft recipient sites, newly sutured wounds, abrasions, and minor or partial thickness burns. It may also be used as an initial layer in dressing surgical wounds with light exudate.

## 3 STUDY DESIGN

### 3.1 OVERALL DESIGN

This study will be a single-center, randomized, parallel-assignment clinical trial to assess the efficacy of using single-use negative pressure wound therapy (NPWT) devices on free flap donor sites. The study duration is approximately 12 months and the subject duration is approximately 30 days.

The primary objective of this study is to assess the progression of wound healing from Baseline through 30 days.

There are 2 arms of the study:

1. *Treatment Group*: PICO Single Use Negative Pressure Wound Therapy System
2. *Control Group*: conventional dressing of xeroform gauze and padding

### 3.2 END OF STUDY DEFINITION

A participant is considered to have completed the study if he or she has completed all phases of the study including the last visit or the last scheduled procedure shown in the Schedule of Activities (SoA), Section 1.2.

The end of the study is defined as completion of the last visit or procedure shown in the SoA in the trial globally.

## 4 STUDY POPULATION

### 4.1 INCLUSION CRITERIA

In order to be eligible to participate in this study, an individual must meet all of the following criteria:

1. Male or female, aged 18 or older
2. Able to consent for themselves
3. Undergoing reconstructive surgery requiring split-thickness skin graft coverage of a free flap donor site (i.e., radial forearm free flap or fibula free flap)

### 4.2 EXCLUSION CRITERIA

An individual who meets any of the following criteria will be excluded from participation in this study:

1. Less than 18 years of age
2. Unable to consent for themselves
3. Undergoing reconstructive surgery that does not require split-thickness skin graft coverage of a free flap donor site

### 4.3 SCREEN FAILURES

Screen failures are defined as participants who consent to participate in the clinical trial but are not subsequently randomly assigned to the study intervention or entered in the study. A minimal set of screen failure information is required to ensure transparent reporting of screen failure participants, to meet the Consolidated Standards of Reporting Trials (CONSORT) publishing requirements and to respond to queries from regulatory authorities. Minimal information includes demography, screen failure details, eligibility criteria, and any serious adverse event (SAE).

Individuals who do not meet the criteria for participation in this trial (screen failure) may not be rescreened.

### 4.4 STRATEGIES FOR RECRUITMENT AND RETENTION

Patients who have presented to the UAB Department of Otolaryngology for evaluation and treatment of head and neck disorders requiring surgery. The Principal Investigator and sub-investigators have practices specifically designated for treating head and neck disorders, with potential for enrollment.

Subjects will be identified from individuals treatment by the investigators in their clinics. Potential subjects will be approached by the Principal Investigator or qualified research staff authorized to conduct the informed consent discussion during their regularly-scheduled clinic visit about participation in the study.

## 5 STUDY INTERVENTION

### 5.1 STUDY INTERVENTION(S) ADMINISTRATION

#### 5.1.1 STUDY INTERVENTION DESCRIPTION

All study interventions are FDA-cleared, commercially available, and will be used in accordance with approved labeling. No modifications have been performed for this study.

##### Treatment Group

510(k) Number: K151436

Trade/Device Name: Pico Single Use Negative Pressure Wound Therapy System

Regulation Number: 21 CFR 878.4780

Regulation Name: Powered suction pump

Regulatory Class: Class II

Product Code: OMP

PICO Single Use Negative Pressure Wound Therapy System is a small, lightweight, portable suction device consisting of an electric motor driven, twin-diaphragm, vacuum pump connected to a super-absorbent, gentle adhesive dressing. The pump, dressing and secondary fixations strips are supplied sterile and single use. The dressing is applied to the wound and secondary fixation strips are placed over the outside edges to help hold the dressing in place. When the suction pump is turned on, air is pulled out of the dressing creating negative pressure and drawing excess fluid from the wound into the dressing. The pump is battery operated and is supplied with two AA lithium batteries which provide up to 168 hours (7 days) of battery life depending upon leak rate. The batteries can be replaced if required. The pump is programmed to stop working after 168 hours (7 days) of use and will not re-start after this time, even with new batteries. Negative pressure will not be applied at this point.

##### Control Group

510(k) Number: K152970

Trade/Device Name: Dynarex Xeroform Petrolatum Dressing

Regulatory Class: Unclassified

Product Code: FRO

The Dynarex Xeroform Petrolatum Dressing is a sterile, single use, non-adherent dressing consisting of non-woven absorbent gauze saturated with Xeroform with 3% Bismuth Tribromophenate in a petrolatum blend. Packaged in paper metalized chevron pouches and available in several sizes.

### 5.2 MEASURES TO MINIMIZE BIAS: RANDOMIZATION

Subjects will be randomized 1:1 (parallel assignment) into the two treatment groups. The next subject to be randomized into a trial will receive the treatment corresponding to the next free number in the

randomization schedule. The appropriate number and associated treatment for the next subject will only be allocated when entry of that subject to the randomized part of the trial has been confirmed.

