### 5.3 STUDY INTERVENTION COMPLIANCE

*Define how adherence to the protocol (e.g., administration of study intervention, use of device,) will be assessed, and verified (if applicable, e.g., plasma assays, electronic monitoring devices, daily diaries). Include a discussion of what documents are mandatory to complete (e.g., participant drug log) and what source documents/records will be used to calculate study intervention compliance.*

For both the Treatment Group and the Control Group, the dressings will remain in place until post-op day (POD) #5. Following dressing removal on POD #5, participants in both groups will be given identical wound management instructions. Photographs of each participant's healing wound will be obtained on POD #5 (+1 day) and on their first post-op clinic visit, approximately POD #14-21, and at POD #30 (+7 days). Participants who do not come to their designated follow-up appointments will be dropped from the dataset.

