## 8 STATISTICAL CONSIDERATIONS

### 8.1 STATISTICAL HYPOTHESES

Primary Endpoint(s): Progression of wound healing, as measured by comparison of photographs of all subject wounds taken at post-operative Day 5, post-operative Day 14-21, and post-operative Day 30. Percentage skin graft take will be evaluated on Day 30 by blinded, independent raters.

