### 8.2 SAMPLE SIZE DETERMINATION

Our statistics indicate that assuming an 80% graft take, the number of patients needed for an appropriately powered study (80%) would be 44 patients in each group; however, we plan to only recruit 20 participants total, making this more of a pilot study to see if it's worthwhile to pursue a larger, prospective randomized controlled trial, given the costs associated with the devices to be used in this study.

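### Does a 20-patient pilot with two donor-site types need randomization stratified by donor site?

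*Combined protocol and SAP*

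**What the plan says.** Section 5.2 gives the allocation rule: "Subjects will be randomized 1:1 (parallel assignment) into the two treatment groups". The mechanism is sequential: "The next subject to be randomized into a trial will receive the treatment corresponding to the next free number in the" randomization schedule. No stratum, block size or minimization factor is named there or elsewhere.

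Two donor-site types can enter. Section 4.1 requires "Undergoing reconstructive surgery requiring split-thickness skin graft coverage of a free flap donor site (i.e., radial forearm free flap or fibula free flap"), and the Synopsis describes the same population. The expected mix is not given.

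The outcome concerned is in Section 8.1: "Percentage skin graft take will be evaluated on Day 30 by blinded, independent raters". Section 8 gives donor site no role in the comparison. Section 8.2 states the scale and purpose: "we plan to only recruit 20 participants total, making this more of a pilot study", meant to show whether a larger trial is worth doing.

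**The concern.** Donor site is known before surgery, has two levels, and could plausibly affect how well a graft takes. In a trial of 20, one unstratified list can put, say, 7 forearm patients in one arm and 3 in the other. If take differed by site, part of the observed arm difference would then reflect site rather than dressing. The plan provides no control for site at allocation or in the analysis. The result is meant to inform a decision about a larger trial, so a misleading arm difference could matter. Two short lists, one per site, look like a free remedy.

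**Working it through.** **Inputs.** From the documents: 20 patients and 1:1 allocation (Sections 8.2 and 5.2), and two site types (Section 4.1). Assumed, because the documents give none: exactly 10 per arm, the forearm share q, the gap in mean take between sites, and the within-site SD. The plan states no figure of its own on this point. The 44 per group in Section 8.2 plays no part in it.

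**Step 1. How likely is imbalance?** Let K of the 20 patients share one site and X of them fall in the first arm. X is hypergeometric (20, K, 10), and the site counts differ between arms by |2X − K|. For K = 10, a difference of 4 or more means X ≤ 3 or X ≥ 7:

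2 × (120² + 45² + 10² + 1²) / 184,756 = 33,052 / 184,756 = 17.9%.

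| K at the less common site | 3 | 4 | 5 | 6 | 7 | 8 | 9 | 10 |
|---|---|---|---|---|---|---|---|---|
| P(difference ≥ 4) | 0% | 8.7% | 3.3% | 14.1% | 5.7% | 17.0% | 7.0% | 17.9% |

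Averaged over K ~ Binomial(20, q), this is 11.5%, 8.5% and 4.8% for q = 0.5, 0.7 and 0.8. Unstratified permuted blocks of 2, 4, 10 or 20 give the same values within simulation error.

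**Step 2. What would an imbalance do?** With 10 per arm, a difference of 4 shifts the arm difference by (4/10) × gap: 0, 2, 4 or 8 points for gaps of 0, 5, 10 or 20. The shift is as likely to favor one arm as the other. The ordinary standard error already contains this variation:

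SE = √[0.2 × (SD² + gap² × q(1 − q))].

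For gap 10, SD 15 and q = 0.5 this is √[0.2 × (225 + 25)] = 7.1 points. The 95% half-width is 2.101 × 7.07 = 14.9 points (18 df), against a shift of 4. The uncertainty from site mix is therefore already in the interval, and type I error stays near 5%.

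**Step 3. What does stratifying itself add?** The gain has to be split between adjusting for site and stratifying by it. Changes in SE relative to an unstratified, unadjusted comparison (simulated, blocks of 2 and 4 within site for the stratified case):

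| Case | Unstratified list, adjusted | Stratified and adjusted |
|---|---|---|
| No gap | about 3% worse | 0.4-0.7% worse |
| Gap 20, SD 15, q = 0.5 | 14.3% better | 16.5% better |

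In the second row the unadjusted SE is 8.06. It becomes 8.06 × 0.857 = 6.91 with adjustment alone and 8.06 × 0.835 = 6.73 with both. The ratio is 6.73 / 6.91 = 0.974, so stratifying contributes 2.6%. Over q = 0.5 to 0.8 the contribution is about 2-2.6%, whatever the gap. At a gap of 10, stratifying and adjusting together are worth 1-5%.

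**Step 4. What does it cost?** Small blocks within site keep the running totals close, so anyone who sees past allocations can guess that the under-represented arm comes next. Block sizes need not be known. By simulation that guess is right for about 71% of allocations with concealed blocks of 2 and 4 within site, about 62% with one list balanced only at 20, and 50% under simple randomization. Section 3.1 describes a single center, and the surgical team sees each dressing. Arms of 11 and 9 would also occur about 35% of the time, but that raises the SE only by √[(1/11 + 1/9)/0.2] − 1 = 0.5%.

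**The case for a change.** The best case for stratifying is that the imbalance probabilities could be larger than those above. Section 5.2 does not guarantee a 10:10 split. Under simple randomization the chance of a difference of 4 or more at K = 10 is 34%. Section 6.2 allows some replacements, and Section 5.3 says "Participants who do not come to their designated follow-up appointments will be dropped from the dataset", so the split can also shift after randomization. Two lists with blocks of 2 and 4 hold the within-site difference at randomization to 2 at most. They need no extra patients and cost one degree of freedom (critical t 2.101 to 2.110).

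The arithmetic stands, and so does the reading that no stratum is described. But a higher chance of imbalance matters only if site affects take, and the documents give no ground for assuming that. Sections 2.1 and 2.2 discuss free flap donor sites as one class. Loss to follow-up does not clearly worsen the picture: with 8 left per arm the averaged probabilities are about 8%, 5% and 3%, although a difference of 4 then moves the result by 0.5 rather than 0.4 times the gap. The claim that the safeguard is nearly free does not stand, because it ignores predictability. That cost would disappear if the existing list already used small blocks, but the block size is not stated.

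Section 8 names no test or model for the Day 30 comparison. That is a separate matter, and whether to adjust for site is a detail within it.

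**Conclusion.** The concern does not hold as a criticism of the plan. One unstratified 1:1 schedule gives a valid comparison, and no statement or figure in the documents is wrong on this point. A site difference of 4 or more has a 0-18% chance with exactly 10 per arm, and more under simple randomization. Its effect is random in direction, already reflected in the standard error, and zero if take does not differ by site. Stratification would improve precision by about 2-2.6% beyond adjustment, in exchange for more predictable allocation at one center with an unblinded surgical team. Reasonable statisticians would choose differently here. The effect sizes rest on assumed site gaps of 0-20 points, SDs of 15-20 and a forearm share of 50-80%. Evidence that take differs strongly by site would strengthen the case for stratifying, but the documents contain none.

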### 5.3 STUDY INTERVENTION COMPLIANCE

*Define how adherence to the protocol (e.g., administration of study intervention, use of device,) will be assessed, and verified (if applicable, e.g., plasma assays, electronic monitoring devices, daily diaries). Include a discussion of what documents are mandatory to complete (e.g., participant drug log) and what source documents/records will be used to calculate study intervention compliance.*

For both the Treatment Group and the Control Group, the dressings will remain in place until post-op day (POD) #5. Following dressing removal on POD #5, participants in both groups will be given identical wound management instructions. Photographs of each participant's healing wound will be obtained on POD #5 (+1 day) and on their first post-op clinic visit, approximately POD #14-21, and at POD #30 (+7 days). Participants who do not come to their designated follow-up appointments will be dropped from the dataset.

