## 6 STUDY INTERVENTION DISCONTINUATION AND PARTICIPANT DISCONTINUATION/WITHDRAWAL

### 6.1 DISCONTINUATION OF STUDY INTERVENTION

Discontinuation from the study intervention (PICO vs xeroform dressing) does not mean discontinuation from the study, and remaining study procedures should be completed as indicated by the study protocol. If a clinically significant finding is identified (including, but not limited to changes from baseline) after enrollment, the investigator or qualified designee will determine if any change in participant management is needed. Any new clinically relevant finding will be reported as an adverse event (AE).

The data to be collected at the time of study intervention discontinuation will include the following:

- Wound photograph
- Assessment of adverse events
- Assessment of concomitant medications

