### 6.3 LOST TO FOLLOW-UP

A participant will be considered lost to follow-up if he or she fails to return for 2 scheduled visits and is unable to be contacted by the study site staff.

The following actions must be taken if a participant fails to return to the clinic for a required study visit:

- The site will attempt to contact the participant and reschedule the missed visit and counsel the participant on the importance of maintaining the assigned visit schedule and ascertain if the participant wishes to and/or should continue in the study.
- Before a participant is deemed lost to follow-up, the investigator or designee will make every effort to regain contact with the participant (where possible, 3 telephone calls and, if necessary, a certified letter to the participant's last known mailing address or local equivalent methods). These contact attempts should be documented in the participant's medical record or study file.
- Should the participant continue to be unreachable, he or she will be considered to have withdrawn from the study with a primary reason of lost to follow-up.

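### Section 5.3 drops randomised participants from the dataset for missed follow-up without saying how many missed visits count; if one is enough, observed Day 30 graft takes are deleted.

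*Combined protocol and SAP*

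**What the plan says.** Section 5.3 lists three photograph times: POD 5, a second photograph "on their first post-op clinic visit, approximately POD #14-21", and POD 30. It then states: "Participants who do not come to their designated follow-up appointments will be dropped from the dataset". It does not say whether one, two or all appointments must be missed, or whether the dataset means all of a participant's data or one analysis.

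Section 8.1 describes the primary endpoint as progression of healing, by "comparison of photographs of all subject wounds taken at post-operative Day 5, post-operative Day 14-21, and post-operative Day 30". It adds: "Percentage skin graft take will be evaluated on Day 30 by blinded, independent raters". Percentage take is specified at no other time. The rest of Section 8 is the sample size paragraph (8.2), so there is no analysis population, intention-to-treat statement or missing-data method.

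Section 6.3 has a different rule. A participant is lost to follow-up if he or she "fails to return for 2 scheduled visits and is unable to be contacted by the study site staff". After a single missed visit, "The site will attempt to contact the participant and reschedule the missed visit".

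Section 8.2 plans 20 participants in total and Section 5.2 allocates them 1:1, so about 10 per arm. Under Section 6.2, participants who leave the study after receiving the intervention are not replaced.

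**The concern.** Attendance is behaviour after randomisation, and it may be related to how the wound is healing or to the dressing received. Removing people on that basis can leave two groups that are no longer the randomised arms. Some loss cannot be avoided, because a participant who never attends Day 30 has no take to analyse. The difficulty with Section 5.3 is that it may also remove people whose Day 30 take was observed, because they missed an earlier visit.

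A missed POD 14 visit does leave a gap in the progression comparison. It is no reason to delete the same participant's Day 30 take.

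The missing threshold is a second problem. Someone must decide how many missed visits count and whether a rescheduled visit counts as attended. The plan allows that decision to be made after data are available. With about 10 per arm, including or excluding one or two people can visibly move the result.

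**Working it through.** The plan gives no figure for missed visits or exclusions, so there is nothing to reproduce. The check asks how many observed Day 30 takes each reading of Section 5.3 would delete.

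**Inputs**
- N = 20 (Section 8.2), 1:1 (Section 5.2).
- Two clinic visits count in the base case, POD 14 and Day 30, because Section 5.3 calls the POD 14-21 visit the first post-op clinic visit. POD 5 is added as a variant.
- Assumption: q = probability of missing a given visit after any rescheduling, taken as 0.05, 0.10 and 0.15.
- Assumption: r = correlation between missing POD 14 and missing Day 30, taken as 0 and 0.5.

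**Reading 1: one missed visit is enough.** A Day 30 take is deleted when POD 14 is missed and Day 30 is attended. That probability is p = q(1 − q)(1 − r). The expected number deleted is 20p, and the chance of deleting at least one is 1 − (1 − p)^20.

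| q | r | p | Expected deleted | Chance of at least one |
|---|---|---|---|---|
| 0.05 | 0 | 0.0475 | 0.95 | 62% |
| 0.10 | 0 | 0.0900 | 1.80 | 85% |
| 0.15 | 0 | 0.1275 | 2.55 | 93% |
| 0.05 | 0.5 | 0.02375 | 0.475 | 38% |
| 0.10 | 0.5 | 0.0450 | 0.90 | 60% |
| 0.15 | 0.5 | 0.06375 | 1.275 | 73% |

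If POD 5 also counts, with independent misses, the expected number deleted is 20(1 − q)[1 − (1 − q)²]:
- q = 0.05: 19 × 0.0975 = 1.85
- q = 0.10: 18 × 0.19 = 3.42
- q = 0.15: 17 × 0.2775 = 4.72

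**Reading 2: two missed visits are needed.**
- If only the two clinic visits count, anyone with two misses has missed Day 30, so 0 observed takes are deleted.
- If POD 5 also counts, a take is deleted when POD 5 and POD 14 are both missed and Day 30 is attended: 20q²(1 − q) = 0.05, 0.18, 0.38.

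**Reading 3: all visits must be missed.** No Day 30 take is deleted. If only the two clinic visits count, an existing POD 5 photograph would still be discarded.

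**Precision.** Take q = 0.10 and r = 0. Day 30 is observed in 10 × 0.9 = 9.0 per arm. Reading 1 keeps 10 × 0.9² = 8.1. The 95% confidence interval half-width for a difference in means, in SD units, is t(0.975, 2n − 2) × √(2/n):
- n = 9: 2.120 × 0.471 = 1.00 SD
- n = 8: 2.145 × 0.500 = 1.07 SD

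**Takes that were never observed.** This example, with assumed values, shows how much they could matter. Each arm of 10 has one missing take, the nine observed average 80% in both arms, the lowest observed take is 40% and the highest 100%. Filling with the lowest gives (9 × 80 + 40)/10 = 76%, and with the highest (9 × 80 + 100)/10 = 82%. Filling one arm low and the other high, then swapping, moves the arm difference from −6 to +6 points around an observed 0.

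**The case against.** The strongest reply is that the harm needs one particular reading. The sentence uses the plural, and Section 6.3 responds to a single miss by rescheduling. It treats a participant as lost only after two misses and failed contact. Read with Section 6.3, Section 5.3 may mean only that people lost to follow-up leave the dataset, and then almost no observed Day 30 take is deleted. The Schedule of Activities also allows ±7 days at both clinic visits, so missed visits may be rare. All the miss rates above are assumptions.

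This stands as a limit on size. It does not settle the text: Section 5.3 does not refer to Section 6.3, gives no count and does not say how a rescheduled visit is treated.

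Two further points carry some weight. The Schedule of Activities places blinded photograph assessment at the end of the study, so attendance is known before take is rated. That reduces the risk of a data-driven choice but does not remove it, because the clinical team sees the wounds earlier and the rule could still be fixed after rating. Section 8.2 also presents the trial as a pilot, with no confirmatory test to invalidate. But its result is meant to inform whether a larger trial is worthwhile, and each of 20 participants counts heavily.

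Finally, analysing only observed Day 30 takes still depends on attending Day 30. That is correct. The fix removes avoidable deletion, and takes never observed remain missing.

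**Conclusion.** The concern holds and should be fixed. Section 5.3 is a rule for excluding participants after randomisation, with no threshold, not reconciled with Section 6.3 and not overridden by Section 8. Followed on the one-visit reading, it deletes observed Day 30 takes. At assumed miss rates of 5% to 15% at the two clinic visits, the expected loss is about 0.5 to 2.6 of 20, depending on how far misses cluster. It is higher if POD 5 also counts, and 0 to 0.38 on the other readings.

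Confidence is high that the rule is undefined and can delete observed outcomes. The number actually deleted cannot be known from the documents, nor can the direction or size of any bias. The case rests on keeping the randomised comparison intact and fixing the rule in advance, since the loss of precision is small.

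**What to change.** 1. Delete the sentence in Section 5.3.
2. State in Section 8 that every randomised participant with an observed Day 30 take is analysed in the assigned arm, whatever earlier visits were missed.
3. State that the progression comparison uses all available photographs. Section 8 will need to define the progression measure for this to be workable.
4. Let Section 6.3 alone define loss to follow-up, and say whether a rescheduled visit counts as attended.
5. Report the number missing Day 30 by arm, with reasons.
6. As an optional addition, name one sensitivity analysis: fill missing Day 30 takes with the lowest take observed in the trial in one arm and the highest in the other, then swap, and report both arm differences.

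The cost is a few sentences in the protocol and a little extra analysis. No extra patients or visits are needed.
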